1.3 Current Standards: Outreach, Screening, and Therapies

- Currently, there is no standard model of public hepatitis C education and screening promotion. Although approaches like newspaper or media advertisement were used in the past, their benefit remains unknown. On the contrary, there are published reports evaluating the benefit of media campaigns on awareness of breast and cervical cancer screenings. Evaluating the benefit of this project is quite challenging, a meta-analysis revealed short term response of 4% to mass education on improving awareness for mammogram and pelvic examination for breast and cervical cancers, respectively¹⁴. There are no prior studies to estimate the response to HCV screening education in the mass population.
- Current standards encourage HCV screening for individuals considered to be at risk. This includes baby boomers, individuals exposed to infected blood or illicit

drug users. However, these standards do not take into consideration the transmission of disease and other possible causes, leaving millions undiagnosed.

- There are a variety of tests that can detect the presence of Hepatitis C Virus, one of which utilizes anti-HCV ELISA test and is confirmed by HCV PCR. Additional methods include imaging studies and liver biopsies.
- Current standards of treatment include several antiviral medicines that effectively cure the disease in most cases. The course of treatment typically takes 12-24 weeks based on the genotype of disease, extent of liver damage and whether the patient was treated for hepatitis C in the past. In addition to antiviral therapy, complications like cirrhosis and subsequent complications can also be treated using different medical procedures or medicines to prevent risk of liver failure, portal hypertension and liver cancer¹³.
- The Arizona Department of Public Health lags three year on their data compilation and reporting. Most recent data available for review is from 2016.

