2.2 Endpoints

Primary Endpoints:

- Patients screened
- Patients treated

Secondary Endpoints:

- Rate of diagnosed HCV+ individuals
- Rate of patients undergoing treatment
- Increased awareness
- > Identify challenges in terms of identification

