3.0 Investigational Plan

3.1 Study Design

- This is a prospective study performed over a 45-month period. The principal design plan will follow Figure 3 below.
- The study design is based on HCV prevalence order, which was determined based on statistical data from the Arizona Department of Health Services and rate of Hepatitis C per 100,000 (Figure 4). High prevalence counties (123+ cases per 100,000) including La Paz, Mohave, and Yavapai with a total targeted population of 391,999 individuals. Medium-prevalence Counties (101-123 cases per 100,000) are Coconino, Gila, Greenlee, Maricopa, Pima and Pinal with total targeted population of 4,724,421. Low-prevalence counties (<101 per 100,000) including Apache, Cochise, Graham, Navajo, Santa Cruz, and Yuma with a population of 490,388.

- For the initial 9 months the study will utilize direct communication methods (email and text messages) to reach high prevalence areas (Month 1-6), medium prevalence areas (Months 7- 12), and low prevalence areas (Month 13-18).
- The second phase of the study will utilize indirect communication methods (Newspapers and Radio advertisements) and similarly target areas of high prevalence (Month 12-24), medium prevalence (Month 25-30) and low prevalence (Month 31-36).
- The third and last phase is detected for shelter visits and homeless education in high prevalence areas (Month 37-39), mid-prevalence areas (Month 40-42) and low prevalence areas (Month 43- 45).
- This program will follow a streamline cascade of care with three complementary, consecutive portions: Patient education during intervention periods, connection to appropriate care and treatment during gap periods (Figure 3).
- The person responsible for conducting and implementing the project will be the program coordinator. The coordinator will be responsible for responding to calls or emails regarding the study in reference to the FAQ in Appendix 8.3. One hour daily, 5 days per week will be dedicated to answering emails and responding to voice messages or calls. The number of hours will be adjusted according to project performance and needs.

Phase 1: Direct Communication

1. Direct Customized Email Messages

Email messages are customizable and tailored to individual people. The expected response rate as compared to similar healthcare content is about 2%, 112,136 of our targeted group.

a. Generating Email List

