3.2 Subjects

The targeted study population consists of the entire Arizona population 15+ years of age. According to the ADHS 2017 vital statistics, this age range makes up 80% of the population and a total of 5,606,808 people. The targeted population is divided and ordered as below based on two parameters: known hepatitis C prevalence rates and risk, and the optimal method of communication.

1. Adults (45+)

Baby boomers are 5 times more likely to have hepatitis C than adults from any other age group⁴. According to AZ DHS population statistics, this group makes up 51% of the targeted population; 2,864,689 people. We hypothesize that older people are not exposed to social media as adolescents and young adults are. Therefore, it is important to utilize Email, direct text messages and newspaper outreach to reach this population.

2. Nasal and Injection Drug Users

Another extremely high-risk subgroup is nasal and injection drug users. Figure 5 below shows the rate of HCV positive antibody tests compared to the percentage tested categorized by risk factors. The results indicate 88% of the HCV positive clients had history of nasal drug use compared to 69% amongst all clients¹. We believe reaching out to this community would be an essential step in diminishing hepatitis C. To reach out to this group we plan on distributing pamphlets to treatment and rehabilitation entities.

3. Homeless

Another high-risk subgroup likely to develop infectious diseases is the homeless. According to Phoenix Rescue Mission, there are over 36,000 homeless people in Arizona, 71% of which are in Maricopa county⁸. In addition to their lack of awareness, this group likely do not have access to healthcare or healthy living environments, making them even more prone to fatal viruses and diseases. The most appropriate method to reach this subgroup would be through homeless shelter visits.

4. Adults (20-44)

This age groups makes up about 40% of the targeted population; 2,273,230 people. This group is likely exposed to social media as well as newspapers and direct communication methods such as email and text messages.

5. Millennials / Adolescents (<19 years of age)

We believe this age group, consisting of 8% of the targeted population; 468,889 people, would be equally responsive to social media and directed Emails and text messages. With the growing impact social media has on this category, it has more potential of engaging them than any other means of communication would.

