3.5 Links to Care: Treatment of HCV Infection

- In case of a positive test results, the project coordinator will communicate with the patients for treatment options.
- Patients with HCV+ screening results will be contacted during the gap periods by the program coordinator, who will link these patients to treatment and care.
- Project coordinator will identify HCV care provider for each HCV positive patient depending upon patient's insurance status.
- Project coordinator will help and facilitate assistance program applications to patients without insurance.
- > The screening process is shown in Figure 6.

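### The 45-month calendar ends with the last Phase 3 tier and no per-person window is set, so late-found positives can be counted as untreated on a primary endpoint

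*Protocol*

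**What the plan says.** Protocol 2.2 lists "Patients treated" as a primary endpoint and "Rate of patients undergoing treatment" as a secondary one. Neither entry says whether a person counts on starting or on completing treatment, or within what time.

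Protocol 3.1 fixes the calendar: "This is a prospective study performed over a 45-month period". Phase 3 begins with "shelter visits and homeless education in high prevalence areas (Month 37-39") and continues with "mid-prevalence areas (Month 40-42) and low prevalence areas (Month 43- 45"). The last outreach tier therefore closes in the last month of the study. Section 5.2 places the analysis at the end of the study.

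On the path to treatment, section 3.5 says: "Patients with HCV+ screening results will be contacted during the gap periods by the program coordinator". Section 1.3 gives the length of treatment: "The course of treatment typically takes 12-24 weeks".

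Section 5.3 expects the share of positives who are treated to rise from 26.1% to about 30%. The synopsis says that methods will be compared on diagnostic rates, and that rates of linkage to care will be used to find deficits in treatment.

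**The concern.** A person who tests positive through a Phase 1 text message can be followed for treatment for more than two years. A person who tests positive at a shelter visit in Month 44 has at most about a month, and linkage contact may not happen until the final gap. With no common window, anyone not yet treated when observation stops is counted as untreated.

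Two readings of the results are at stake. The first is the overall treated rate against the expected rise of about four percentage points, a margin small enough for a cut-off effect to matter. The second is the search for deficits in care. A low treated rate among shelter and NA/AA attendees, whom section 3.2 treats as high-risk, could be read as a failure of linkage when it only reflects where the calendar stops.

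**Working it through.** **Inputs.** Tier closing months and target populations by tier are from Protocol 3.1; course length is from 1.3; 26.1%, 30% and a flat yield of 464 positives per month are from 5.3. The linkage delay is not given, so 0-3 months is assumed. Section 3.1 is not consistent about when some phases start, but only closing months are used here.

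**The stated duration reproduces.** 18 (Phase 1) + 18 (Phase 2) + 9 (Phase 3) = 45 months. Nothing remains after the last tier.

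**Time left after tier close** = 45 - closing month.

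| Tier | Phase 1 | Phase 2 | Phase 3 |
|---|---|---|---|
| High | 45 - 6 = 39 | 45 - 24 = 21 | 45 - 39 = 6 |
| Medium | 45 - 12 = 33 | 45 - 30 = 15 | 45 - 42 = 3 |
| Low | 45 - 18 = 27 | 45 - 36 = 9 | 45 - 45 = 0 |

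**Course length in months.** At 30.4375/7 = 4.348 weeks per month, 12 weeks = 2.76 months and 24 weeks = 5.52 months. A course completed by Month 45 must start by 45 - 2.76 = 42.24 or 45 - 5.52 = 39.48.

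**Share of Phase 3 positives cut off.** Assume positives arise evenly over each 3-month tier (the low tier runs from time 42 to 45) and the clock starts at the positive test. A person is cut off if test time + delay + course exceeds 45. The total is weighted by tier time (one third each) and by target population (391,999, 4,724,421 and 490,388 of 5,606,808, or 7.0%, 84.3% and 8.7%).

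| Treated means | Delay | High | Medium | Low | By time | By population |
|---|---|---|---|---|---|---|
| Started | 0 | 0% | 0% | 0% | 0% | 0% |
| Started | 1 month | 0% | 0% | 33% | 11% | 3% |
| Started | 3 months | 0% | 0% | 100% | 33% | 9% |
| 12 weeks completed | 0 | 0% | 0% | 92% | 31% | 8% |
| 12 weeks completed | 1 month | 0% | 25% | 100% | 42% | 30% |
| 12 weeks completed | 2 months | 0% | 59% | 100% | 53% | 58% |
| 24 weeks completed | 0 | 0% | 84% | 100% | 61% | 80% |
| 24 weeks completed | 1 month | 17% | 100% | 100% | 72% | 94% |

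More than half of Phase 3 is cut off only when delay plus course exceeds about 4.5 months (19.5 weeks).

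**Starting the clock at linkage contact instead.** Assume the two-months-on, one-month-gap pattern of section 3.1 also holds in Phase 3. Low-tier contact then falls in Month 45, so nobody in that tier can complete even 12 weeks, and a one-month delay to start removes the whole tier. Medium-tier contact falls in Month 42 (time 41-42): everyone can complete 12 weeks with no delay (42 + 2.76 = 44.76) and nobody can complete 24 weeks (41 + 5.52 = 46.52). The synopsis instead describes one month on and a two-month gap. On that pattern the completion results are the same, and a one-month delay to start removes half of the low tier.

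**Effect on the treated rate.** Assume an equal yield of positives in all 45 months and a true rate of 30%. With the clock at the positive test, the last (delay + course) months of positives go uncounted, so observed rate = 30% × (45 - delay - course)/45.

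- Started, 1-month delay: 30% × 44/45 = 29.3%
- 12 weeks completed, no delay: 30% × 42.24/45 = 28.2%
- 24 weeks completed, no delay: 30% × 39.48/45 = 26.3%

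The last case removes nearly all of the expected gain over 26.1%. It is illustrative, because yield by phase is not given.

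**The case against.** **Comparison of methods.** A reader might infer that the comparison of methods is biased against Phase 3. The documents do not support that. The synopsis ranks methods on diagnostic rates, and section 3.1 measures Phase 3 impact by screening and test results. Neither depends on how long treatment lasts. A separate route remains: the synopsis lets people use the screening code some months after receipt, so tests by last-tier recipients could fall after Month 45. That concerns test timing, not course length.

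**Most of Phase 3.** A reader might also infer that most of Phase 3 is lost, pointing out that the medium tier contains Maricopa and that, of the state's homeless people, "71% of which are in Maricopa county". This holds only if treated means completed and delay plus course exceeds about 4.5 months from the positive test. The wording of the secondary endpoint suggests receipt of treatment, and the course length appears only in background text. Weighting by population also cuts both ways: it lowers the 12-week, no-delay loss from 31% to 8% and raises the 24-week loss from 61% to 80%.

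**Data cut.** That data end at Month 45 is inferred. Section 5.1 mentions an end-of-study collection phase without a date, and the design figure is not shown. If treatment status were recorded only at each tier's own gaps, the early phases would not have the long advantage tabulated above. This objection stands as a limit on the finding. It does not remove it, because the protocol states neither a common window nor any follow-up after the last tier.

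**Unseen analysis plan.** The SAP might define treated. The calendar, however, is fixed in the protocol, and it truncates the last tier under any definition that involves a delay.

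**Conclusion.** The point holds in a limited form. As written, the calendar gives the low-prevalence Phase 3 tier no follow-up, whereas every Phase 1 and Phase 2 tier has at least 9 months, and the primary endpoint sets no window to even this out.

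- **Completed:** 92-100% of the low tier is lost. The medium tier loses none at 12 weeks with no delay and 84% at 24 weeks (all of it if the clock starts at gap contact). The high tier is untouched unless a long course is combined with a delay.
- **Started:** the loss is confined mainly to the low tier and runs from none to all of it as the delay goes from 0 to 3 months.

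The bias is downward. It affects the treated rate, its comparison with 26.1% and about 30%, and any reading of late Phase 3 people as a treatment deficit.

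The size rests on treatment status being tracked to study end, observation stopping at Month 45, an even yield within tiers, and an assumed linkage delay.

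**What to change.** 1. State in section 2.2 whether treated means started or completed, and count it within one fixed window from the positive result, the same for all phases.
2. Then do one of the following:
   - restrict treated and linked rates to people whose full window closes by Month 45, and report the others as incomplete, not untreated; or
   - set the data cut for this endpoint one window after Month 45.

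**Cost.** The definition is a sentence. The restricted analysis needs no new data but drops late Phase 3 people: a 3-month window excludes positives after Month 42 (the low tier), and a 6-month window excludes those after Month 39 (the medium and low tiers). If completion is what counts, a 6-month window leaves only 6 - 5.52 = 0.48 months for linkage on a 24-week course, so the later cut is the better choice for a long window.

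The later cut would fall at Month 48 or Month 51 for these two windows, and needs added follow-up of treatment status. Treatment may be given by outside providers, and the consent described in section 3.4 does not mention treatment records. The sponsor should check that the consent covers this.

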1.4 Research Hypotheses

- 1. We hypothesize that aggressive approach to increased awareness of the entire population while providing effective links to care will promote higher screening rates and therefore increase diagnosis rates.
- 2. We hypothesize that providing screening with no charges would ultimately be a costeffective and time-efficient approach towards eradication of the disease. It will facilitate the process and invite more of the population to get screened with resultant increase in the rates of diagnosis and therefore higher treatment rates.
- 3. We hypothesize that creating a central system to link the identified HCV patients to a facility that could provide effective treatment with their insurance plans would help eradicate HCV in a timely and cost-efficient manner.
- 4. We hypothesize that an aggressive educational and treatment approach would minimize onset of new HCV infection in the future.

2.0 Objectives and Endpoints

2.1 Objectives

- To evaluate the net benefit of an aggressive approach utilizing modern day tools to reach the total population of Arizona at both an individual and population level.
- To evaluate the magnitude of increase in diagnosis rates of Hepatitis C with aggressive outreach to eradicate the disease in the state.
- To evaluate the benefit of utilizing a central system that links identified individuals to a treatment center based upon insurance status.

2.2 Endpoints

Primary Endpoints:

- Patients screened
- Patients treated

Secondary Endpoints:

- Rate of diagnosed HCV+ individuals
- Rate of patients undergoing treatment
- Increased awareness
- > Identify challenges in terms of identification

3.0 Investigational Plan

3.1 Study Design

- This is a prospective study performed over a 45-month period. The principal design plan will follow Figure 3 below.
- The study design is based on HCV prevalence order, which was determined based on statistical data from the Arizona Department of Health Services and rate of Hepatitis C per 100,000 (Figure 4). High prevalence counties (123+ cases per 100,000) including La Paz, Mohave, and Yavapai with a total targeted population of 391,999 individuals. Medium-prevalence Counties (101-123 cases per 100,000) are Coconino, Gila, Greenlee, Maricopa, Pima and Pinal with total targeted population of 4,724,421. Low-prevalence counties (<101 per 100,000) including Apache, Cochise, Graham, Navajo, Santa Cruz, and Yuma with a population of 490,388.

- For the initial 9 months the study will utilize direct communication methods (email and text messages) to reach high prevalence areas (Month 1-6), medium prevalence areas (Months 7- 12), and low prevalence areas (Month 13-18).
- The second phase of the study will utilize indirect communication methods (Newspapers and Radio advertisements) and similarly target areas of high prevalence (Month 12-24), medium prevalence (Month 25-30) and low prevalence (Month 31-36).
- The third and last phase is detected for shelter visits and homeless education in high prevalence areas (Month 37-39), mid-prevalence areas (Month 40-42) and low prevalence areas (Month 43- 45).
- This program will follow a streamline cascade of care with three complementary, consecutive portions: Patient education during intervention periods, connection to appropriate care and treatment during gap periods (Figure 3).
- The person responsible for conducting and implementing the project will be the program coordinator. The coordinator will be responsible for responding to calls or emails regarding the study in reference to the FAQ in Appendix 8.3. One hour daily, 5 days per week will be dedicated to answering emails and responding to voice messages or calls. The number of hours will be adjusted according to project performance and needs.

Phase 1: Direct Communication

1. Direct Customized Email Messages

Email messages are customizable and tailored to individual people. The expected response rate as compared to similar healthcare content is about 2%, 112,136 of our targeted group.

a. Generating Email List

Email listings of Arizona residents will be obtained from National Data Group and mass emails will be sent through sendgrid.com.

b. Frequency and Resources

Emails will be sent out daily during intervention periods of 2 months followed by a 1month gap for two rounds for each of the different prevalence groups. A project coordinator at the Liver Institute PLLC will assure expectations and targeted numbers are met.

c. Email Content

The email content will follow the template in Appendix 8.1, including an introduction of the program coordinator, introduction to the project as well as brief background information on

the disease and its risk factors (Appendix 8.6). It will also include the steps that need to be taken and contact information to answer any questions.

d. Progress Monitoring

Updates will be obtained from the carrier company as documented proof of the number of emails sent. Information will also be collected on how many emails were rejected and how many were opened. This information will then be used to guide adjustments of upcoming steps if expected response rates are not reached.

2. Direct Text Messages

Response rates to text messages are similar to that of emails at about 2% or 112,136 of the targeted population.

a. Generating Phone List

A list of Arizona residents phone numbers will be generated by National Data Group and messages will be sent to the targeted population through Verizon wireless.

b. Frequency and Resources

Text messaging will similarly follow the protocol described in Figure 3. Messages will be sent daily during the intervention period for 2-month followed by a 1-month gap for two rounds for each of the different prevalence groups.

c. Text Content

The text content will follow the template in Appendix 8.2. The message will be brief in comparison to the email content. It will include an introduction of the program coordinator, introduction to the project, the steps that need to be taken to get screened and a link to more information and background on the disease. It will additionally include contact information to answer any questions or connect to screening and treatment resources.

d. Progress Monitoring

Updates will be obtained from the carrier companies as to how many messages were sent daily and how many were rejected. This information will then be used to guide further changes or alterations if expected response rates are not reached.

Phase 2: Indirect Communication

1. Newspapers, Advertisement Content, and Duration

Newspaper advertisements are assumed to generate a response rate of 2% or 112,136 of the targeted population. However, according to the local newspaper statistics, the response rate is expected to be higher.

a. Newspapers

The most common local newspaper in Arizona is The Arizona Republic. Both newspapers are well-rounded, published daily or weekly and readily available to the public. This newspaper serves all counties in Arizona, making it efficient and more accessible to all members of the population.

The Arizona Republic – Best Life

According to republic media.com, "Best Life" is the section inside the Arizona Republic dedicated for active, healthy adults and include preventative health tips and postings. This section is published weekly on Mondays and typically generates 46% response rate from the reader population.

The Arizona Republic – Overview

Since the previous section focuses on health-conscious individuals, another post will be published in the overview section, which is distributed daily. According to republicmedia.com, this section reaches 1.1. million adults weekly in the Phoenix area, 32% of local residents. Advertising through the Arizona Republic is therefore likely to generate the expected response rate and reach the majority of our targeted population.

- b. Duration and Monitoring
 - The hepatitis C newspaper advertisement will run similarly to other communication methods during the intervention periods; in 2-month intervals followed by 1-month gap for two rounds for each of the different prevalence groups.
 - Data collection and monitoring will be based on screening numbers during the gap periods. The project coordinator will be responsible for communicating with the magazine to make adjustments as needed.
- c. Advertisement Content
 - The content of the newspaper advertisement will be an infographic designed to present background information on the disease, a brief explanation of the program and its rationale and next steps that need to be taken.
 - The infographic will be designed by the program coordinator to display the information in a simple and clear format to comply with the newspaper's requirements.

2. Social Media

The third approach aimed to target the remaining 33%; 835,414 is social media: including radio and YouTube advertisements. This method is expected to generate a response rate of about 2%.

a. YouTube ➤ Type of Advertisement

Bumper advertisements are only six seconds and play before videos. Since our target population consists of the entire population of Arizona, the ad will be constricted by location to only appear to viewers from the State of Arizona.

Resources and Content

Since TrueView video has longer duration than bumper ads, it will be more detailed and include a combination of project introduction and rationale along with contact information and links to more information. The bumper ad on the other hand is limited to 6 seconds and will therefore be more concise. Both videos will provide links for more information and connections to screening locations and communication methods to answer any questions in relation to the study.

Frequency and Implementation

The YouTube advertisement will similarly run for 2-month intervals followed by a 1month gap for two rounds for each of the different prevalence groups. The frequency will be determined in accordance with agent feedback and adjusted according to performance thereafter.

Monitoring

By utilizing a Google AdWords account, we will monitor our TrueView ad performance and views. This information can be used to optimize and to adjust throughout the duration of the study if needed.

b. Radio➢ Resources

Radio advertising is one of the powerful means of communication that can reach a large audience from all age groups. The project will therefore employ widely known radio stations in the State of Arizona, one of which is iHeartRadio.

> Content

The content will be like that used in other methods of outreach and will include a brief introduction to the project and its rationale as well as contact information to the project coordinator to answer any questions or inquiries.

Duration and Frequency

The radio advertisement will run in accordance with the other forms of advertising, during intervention periods for 2 months followed by a 1-month gap for two rounds for each of the different prevalence groups. The ads will run 5-7 time per week. The timing will be determined based on feedback from an advertising specialist from iHeartRadio and will be during programs dedicated to the older Arizona population of 40+ years of age.

> Monitoring

LI-HEPC-AZ V1.0 CONFIDENTIAL The radio advertisements will be monitored through regular performance updates of the frequency the advertisements were played over the duration of the study, what time they were played and how many were the expected number of listeners. These updates will guide any mid-study adjustments to the design if needed.

Phase 3: Conferences and Shelter Visits

The final method is educational conferences and visits to homeless shelters and NA/AA meetings. With approximately 0.64% of the population being homeless and 67% of HCV cases with a history of intravenous drug use¹, conference visits are expected to reach the remaining population.

a. Approaches

The first method of reaching this group is through educational visits to homeless shelters and NA/AA meetings in Arizona. There are 22 homeless shelters in the Phoenix area and 14 in Tucson.

b. Conference Visits Frequency

The shelter and NA/AA visits will be conducted during the intervention periods of the study with an anticipated average of three visits per shelter.

c. Monitoring

To monitor the progress of this step the number of attendees to each conference meeting will be recorded. The impact on the other hand will be measured through the screening and test results during the gab period.

